7.1.4.1.2 Lost to Follow-up

If a subject fails to return to the clinic for a required study visit and/or if the site is unable to contact the subject, the following procedures are to be performed:

- The site must attempt to contact the subject and reschedule the missed visit. If the subject is contacted, the subject should be counseled on the importance of maintaining the protocol-specified visit schedule.
- The investigator or designee must make every effort to regain contact with the subject at each missed visit (eg, phone calls and/or a certified letter to the subject's last known mailing address or locally equivalent methods). These contact attempts should be documented in the subject's medical record.
- Note: A subject is not considered lost to follow-up until the last scheduled visit for the individual subject. The amount of missing data for the subject will be managed via the prespecified data handling and analysis guidelines.

7.1.4.2 Subject Blinding/Unblinding

This is an open-label trial; there is no blinding for this trial.

Protocol/Amendment No.: 001-08

7.1.4.3 Domiciling

Subjects in Part I (Arms 1 2, and 3) will report to the CRU on C1D1 and will remain for inpatient observation for at least 24 hours post MK-1454 administration on C1D1. The inpatient observation period post MK-1454 administration on C1D1 may be extended to 48 hours, based on the discretion of the investigator, and/or local IRB/IEC, and/or Health Authority mandate.

This requirement may be waived at the discretion of the Sponsor and will be communicated to sites via a memorandum.

Subjects in Part II (Expansion Cohorts A, B, and C) will report to the CRU on C1D1 and will remain in the clinic for at least 8 hours post MK-1454 administration on C1D1. The observation period post MK-1454 administration on C1D1 may be extended based on the discretion of the investigator and/or local IRB/IEC, and/or Health Authority mandate.

7.1.4.4 Calibration of Equipment

The investigator or qualified designee has the responsibility to ensure that any device or instrument used for a clinical evaluation/test during a clinical trial that provides information about inclusion/exclusion criteria and/or safety or efficacy parameters shall be suitably calibrated and/or maintained to ensure that the data obtained is reliable and/or reproducible. Documentation of equipment calibration must be retained as source documentation at the trial site.

7.1.5 Visit Requirements

Visit requirements are outlined in Section 6.0 – Schedule of Activites. Specific procedurerelated details are provided above in Section 7.1 - Trial Procedures.

7.1.5.1 Screening

Up to 28 days prior to treatment allocation/randomization, potential subjects will be evaluated to determine if they fulfill the entry requirements as set forth in Section 5.1. Tests performed as part of routine clinical management prior to the subject signing consent are acceptable in lieu of a screening test, if these tests are performed within the specified time frame of 28 days prior to treatment allocation/randomization. Bone marrow biopsy results for lymphoma subjects are permissible up to 8 weeks prior to screening.

Screening procedures may be repeated after consultation with the Sponsor.

7.1.5.2 Treatment Period

The treatment period in each treatment arm or expansion cohort (Arm 1, Arm 2, and Arm 3; Cohorts A, B, and C) begins with Cycle 1 and may continue for up to 35 cycles (approximately 2 years) from the start of treatment until disease progression, unacceptable AE(s), intercurrent illness that prevents further administration of treatment, investigator's decision to withdraw the subject, subject withdraws consent, pregnancy of the subject, noncompliance with trials treatment or procedure requirements, or administrative reasons requiring cessation of treatment. Subjects who cross over from Arm 1 to Arm 2 are eligible

MK-1454-001-08 Final Protocol 27-Jul-2021 Confidential

087V73

Protocol/Amendment No.: 001-08

for up to 35 cycles of treatment within Arm 2, regardless of the number of cycles of MK-1454 treatment received in Arm 1. Each cycle includes study drug administration and all associated assessments as outlined in the Schedule of Activities (see Section 6.0).

Specific procedure-related details are provided throughout Section 7.0.

7.1.5.3 Treatment Period Beyond Disease Progression

See Section 7.1.2.7.

7.1.5.4 Discontinued Subjects Continuing to be Monitored in the Trial

The Discontinuation Visit should occur at the time study treatment is discontinued for any reason. If the Discontinuation Visit occurs 30 days from the last dose of study treatment, at the time of the mandatory Safety Follow-up Visit, the Discontinuation Visit procedures and any additional Safety Follow-up procedures should be performed. Visit requirements are outlined in Section 6 - Schedule of Activities. Additional details regarding subject withdrawal and discontinuation are presented in Section 5.8 –Subject Withdrawal/Discontinuation Criteria.

7.1.5.5 30-Day Safety Follow-up Visit

The mandatory 30-day Safety Follow-up Visit should be conducted approximately 30 days (+7 days) after the last dose of trial treatment or before the initiation of a new antineoplastic treatment, whichever comes first. All AEs that occur prior to the 30-day Safety Follow-up Visit should be recorded. Subjects with an AE of Grade >1 will be followed until the resolution of the AE to Grade 0-1 or until the beginning of a new antineoplastic therapy, whichever occurs first.

After the EOT, each subject will be followed for 30 days for AE monitoring and 130 days for SAEs, ECI, and spontaneously reported pregnancy. SAEs, ECI, and spontaneously reported pregnancy will be reported for 30 days after the EOT if the subject initiates new anticancer therapy. Progression of the cancer under study is not considered an AE.

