Subjects who progress by either clinical or radiographic evaluation on monotherapy with MK-1454 (Arm 1), may cross over into the combination therapy arm of MK-1454 and pembrolizumab (Arm 2), provided they meet eligibility criteria. A crossover subject may receive up to 35 cycles of treatment in Arm 2 (MK-1454 with pembrolizumab combination therapy) regardless of the duration of treatment received in Arm 1 (MK 1454 monotherapy).

Subjects treated with monotherapy MK-1454 (Arm 1) may participate in intrasubject dose escalation after the completion of Cycle 3. A subject may undergo dose escalation once during monotherapy with MK-1454. Subjects in Arm 2 may not participate in intrasubject dose escalation. Subjects in Arm 3, an ATD phase, may undergo intrasubject dose escalation one time after receiving 3 cycles of treatment without a \geq Grade 2 drug-related toxicity.

Subjects may continue treatment until one of the following occurs: disease progression, unacceptable AE(s), intercurrent illness that prevents further administration of treatment, investigator's decision to withdraw the subject, subject withdraws consent, pregnancy of the subject, noncompliance with trials treatment or procedure requirements, or administrative reasons requiring cessation of treatment. After the EOT, each subject will be followed up for 30 days for monitoring all AEs. SAEs and ECI will be collected for 130 days after the EOT or for 30 days after the EOT if the subject initiates new anticancer therapy, whichever is earlier.

The Expansion phase (Part II) will open to enroll subjects in Cohorts A to C to evaluate the safety and efficacy of MK-1454 IT in combination with pembrolizumab 200 mg IV. Cohort A will evaluate MK-1454 in 30 subjects with anti-PD-1/PD-L1 refractory HNSCC: Cohort B will include 30 subjects with anti-PD-1/PD-L1 treatment-naïve or refractory TNBC, and Cohort C will include 60 subjects with anti-PD-1/PD-L1 treatment-naïve solid tumors with liver metastases, with a cap at 15 subjects each with colorectal cancer (CRC) or pancreatic cancer. The starting dose for expansion Cohorts A and B will be the preliminary RP2D established in Arm 2. The starting dose and frequency for Cohort C will be the RP2D established for visceral IT administration in Arm 3.

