5.2.3 Dose Modification Due to Adverse Events

The Common Terminology Criteria for Adverse Events, version 4.0 (CTCAE 4.0) must be used to grade the severity of AEs. The investigator may attribute each toxicity event to MK-1454 alone, or to pembrolizumab alone, or to combination therapy. Use dose modification according to Table 11, Table 12, Table 14, or Table 15. If a dose modification for toxicity occurs with MK-1454, the dose may not be re-escalated to the dose that preceded the dose modification. Dose modifications are always based on the previous cycle.

Subjects may have a maximum of 2 dose modifications of MK-1454 throughout the course of the study for toxicities, as described in Section 5.2.3.1. If further toxicity occurs or the criteria for resuming treatment are not met, the subject must be discontinued from the agent. If a subject experiences several toxicities and there are conflicting recommendations, follow the most conservative dose adjustment recommended (dose reduction appropriate to the most severe toxicity).

Protocol/Amendment No.: 001-08

Reduction or holding of one agent and not the other agent is appropriate if, in the opinion of the investigator, the toxicity is clearly related to one of the study drugs. For example, in the combination arms (Arm 2 and Arm 3), if MK-1454 is held due to an AE attributed to that drug, then pembrolizumab may continue to be administered. Appropriate documentation is required regarding which drug the investigator is attributing the AE to. If, in the opinion of the investigator, the toxicity is related to the combination of 2 agents, then both drugs should be held according to recommended dose modifications.

AEs (both nonserious and serious) associated with MK-1454 and pembrolizumab exposure may represent an immunological etiology. These AEs may occur shortly after the first dose or several months after the last dose of treatment.

Exceptional circumstances to following the dose modification tables below may be considered after consultation with the Sponsor.

5.2.3.1 Dose Modification for MK-1454 Drug-related AEs in Part I - Arm 1, Arm 2, and Arm 3

Dose modification guidelines for MK-1454 drug-related AEs are presented in Table 11. In Arm 2, pembrolizumab treatment will be modified for the AEs as described below in . See Table 15 for treatment guidelines for cytokine release syndrome.

Protocol/Amendment No.: 001-08

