- All subjects will be required to provide a sample biopsy of the tumor to be injected with MK-1454 and a sample biopsy from a distant, discrete noninjected site (at least 2 biopsies at each site), unless deemed medically unsafe by the investigator. The sample will be obtained by ultrasound guidance or cross-sectional imaging (CT/MRI) guidance. Method of biopsy will be per guidance of the investigator as well as discussion with the Sponsor. Instructions for tissue collection, processing, and shipment are provided in the Procedures Manual. Leftover main study tissue will be stored for FBR if the subject consents to FBR. Instructions for tissue collection, processing, and shipment are provided in the Procedures Manual.

Protocol/Amendment No.: 001-08

6.1.4 Discontinuation / End of Treatment and Posttreatment Follow-up for Arms 1 to 3

		Posttreatm 30-Day Safety	ent Period Survival	
Trial Period	EOT/ Discontinuation	Follow-up Visit	Follow-up	Notes
Scheduling Day		30 days post last dose	Q12W	
Scheduled Window	±7	+7	±14	
Administrative Procedures				
Prior Medication and Concomitant Medication Review	X	X		
Efficacy Procedures				
Tumor Imaging, RECIST, irRECIST, and/or itRECIST Response Assessment	X			
Medical Photography (Cutaneous Lesions)	X			
IWG Revised Response Criteria for Lymphoma (excluding CTCL)	X			
CTCL Response Criteria	X			
Survival Status Monitoring	\	Updated survival status may be requested by the Sponsor at any time during the course of the study. Upon Sponsor notification, all subjects who do not/will not have a scheduled study visit or study contact during the Sponsor defined time period will be contacted for their survival status (excluding subjects that have a death event previously recorded).		
Safety Assessments and Procedures	See Procedures Manual for collection and management of samples.			
AEs Monitoring	X	X		
Full Physical Examination	X	X		
Weight	X	X		
12-lead ECG		X		T 1
Vital Signs	X	X		Temperature, pulse, respiratory rate, blood pressure, and O ₂ saturation
ECOG Performance Status	X	X		
CBC with Differential	X	X		
Chemistry Panel	X	X		
Lipase and Amylase	X	X		

MK-1454-001-08 Final Protocol
087V73
Confidential

Protocol/Amendment No.: 001-08

		Posttreatm	ent Period	
Trial Period	EOT/ Discontinuation	30-Day Safety Follow-up Visit	Survival Follow-up	Notes
Scheduling Day	EO 17 Discontinuation	30 days post last dose	Q12W	Hotes
Scheduled Window	±7	+7	±14	

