6.2.2 Discontinuation / End of Treatment and Posttreatment Follow-up for Part II – Expansion Cohorts

		Posttreatme	ent Period	
Trial Period	End of Treatment (EOT)/ Discontinuation	30-Day Safety Follow-up Visit	Survival Follow-up	Notes
Scheduling Day		30 days post last dose	Q12W	
Scheduled Window	±7	+7	±14	
Administrative Procedures				
Prior Medication and Concomitant Medication Review	X	X		
Efficacy Procedures				
Tumor Imaging, RECIST, irRECIST, and/or itRECIST Response Assessment	X			
Medical Photography (Cutaneous Lesions)	X			
Survival Status Monitoring	<			Updated survival status may be requested by the Sponsor at any time during the course of the study. Upon Sponsor notification, all subjects who do not/will not have a scheduled study visit or study contact during the Sponsor defined time period will be contacted for their survival status (excluding subjects that have a death event previously recorded). See Procedures Manual for collection
Safety Assessments and Procedures				and management of samples.
AE Monitoring	X	X		
Full Physical Examination	X	X		
Weight	X	X		
12-lead ECG	X			
Vital Signs	X	X		Temperature, pulse, respiratory rate, blood pressure, and O ₂ saturation
ECOG Performance Status	X	X		
CBC with Differential	X	X		
Chemistry Panel	X	X		
Lipase and Amylase	X	X		
Pregnancy Test for WOCBP – Urine or Serum hCG		X		For WOCBP, perform as required locally. If a urine pregnancy test cannot be confirmed as negative, a serum pregnancy test is required.

MK-1454-001-08 Final Protocol 27-Jul-2021 Confidential

Protocol/Amendment No.: 001-08

		Posttreatm	ent Period	
	End of Treatment (EOT)/	30-Day Safety	Survival	
Trial Period	Discontinuation	Follow-up Visit	Follow-up	Notes
Scheduling Day		30 days post last dose	Q12W	
Scheduled Window	±7	+7	±14	
Thyroid Function (TSH, T3, FT3, T4, FT4)		X		
Pharmacokinetics (PK)/Pharmacodynamics/ Future	Biomedical Research/Biomark	ers		See Procedures Manual for collection and management of samples.
Serum for Pembrolizumab PK	X			Only for pembrolizumab-treated
Serum for ADA	X			subjects.
Blood for Plasma Biomarker Analysis	X			
Blood for Serum Biomarker Analysis	X			

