7.1.5.6 Survival Status Monitoring

All subjects, with the exception of those who withdraw consent or are lost to follow-up, will be followed up for survival and will be contacted approximately every 12 weeks (± 14 days) to monitor survival status. Subjects who experience confirmed disease progression or start a new anticancer therapy, will move into the Survival Follow-Up Phase and should be contacted by telephone every 12 weeks to assess for survival status until death, withdrawal of consent, or the end of the study, whichever occurs first.

To ensure current and complete survival data is available at the time of database locks, updated survival status may be requested during the course of the study by the Sponsor. For example, updated survival status may be requested prior to interim and/or final analysis. Upon Sponsor notification, all subjects who do not/will not have a scheduled study visit or study contact during the Sponsor-defined time period will be contacted for their survival

Protocol/Amendment No.: 001-08

status (excluding subjects who have withdrawn consent or have a previously recorded death event in the collection tool).

Every effort should be made to collect information regarding disease status until the start of new antineoplastic therapy, disease progression, death, or the end of the study.

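### SAEs and ECIs are to be collected for 130 days after treatment, but no adverse-event inquiry is scheduled after the 30-day visit, so new non-fatal late SAEs rest on passive reporting

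*Combined protocol and SAP*

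**What the plan says.** **Collection window.** Section 7.1.5.5: "After the EOT, each subject will be followed for 30 days for AE monitoring and 130 days for SAEs, ECI, and spontaneously reported pregnancy". The Trial Summary adds that starting another cancer treatment shortens the window, with the earlier date applying: "SAEs and ECI will be collected for 130 days after the EOT or for 30 days after the EOT if the subject initiates new anticancer" [treatment]. Sections 7.2.3.1 and 7.2.3.2 set the same periods and require reporting to the sponsor within 24 hours.

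**Last safety visit.** Section 7.1.5.5: "The mandatory 30-day Safety Follow-up Visit should be conducted approximately 30 days (+7 days) after the last dose of trial treatment". An earlier start of another antineoplastic treatment brings this visit forward.

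**Schedules.** In 6.1.4 (Arms 1 to 3) the row "AEs Monitoring" is marked at end of treatment and at the 30-day visit. In 6.2.2 (expansion cohorts) the row "AE Monitoring" is marked at the same two points. The Survival Follow-up column carries neither an adverse-event item nor a laboratory test.

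**Later contact.** Section 7.1.5.6 has all subjects who have not withdrawn consent or been lost contacted about every 12 weeks (±14 days). Those with confirmed progression or new therapy "should be contacted by telephone every 12 weeks to assess for survival status until death, withdrawal of consent, or the end of the study".

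**Expected timing.** Section 5.2.3, on events of possible immunological origin: "These AEs may occur shortly after the first dose or several months after the last dose of treatment".

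**The concern.** The text promises 130 days of SAE and ECI follow-up, and Section 7.1.5 leaves visit content to the Schedule of Activities. The schedule delivers an adverse-event inquiry for the first 30 to 37 days only. After that, a site that follows the schedule exactly never asks about adverse events. A subject admitted to another hospital on Day 80 with a serious immune event could stay unrecorded unless the subject or that hospital tells the site.

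Safety is the primary objective (Section 3.1), and Section 8.6.2 summarises AEs by dose level, arm and cohort. If ascertainment is active to Day 30 and passive afterwards, a low count of late SAEs cannot be read as evidence that few occurred.

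**Working it through.** The plan gives no figure of its own to reproduce here. The check is a comparison of the schedules with the text, followed by window arithmetic.

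**Inputs**
- SAE/ECI window: 130 days (7.1.5.5, 7.2.3.1, 7.2.3.2), or 30 days with new anticancer therapy.
- Last scheduled AE monitoring: Day 30, with a window of +7, so up to Day 37 (6.1.4, 6.2.2, 7.1.5.5).
- Survival contact: every 12 weeks = 84 days, ±14 (7.1.5.6). The time origin is not stated.
- Assumption: the end-of-treatment date and the last dose coincide. The sections count from end of treatment, cessation of treatment or last dose. If end of treatment is later, the uncovered stretch is longer.

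**Days without a scheduled AE inquiry** = 130 − day of the 30-day visit
- Visit on Day 30: 130 − 30 = 100 days; 100/130 = 76.9%.
- Visit on Day 37: 130 − 37 = 93 days; 93/130 = 71.5%.

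This applies to subjects who start no new anticancer therapy. For those who do, the SAE/ECI window ends at 30 days and the gap is essentially nil.

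**Where the survival contacts fall** = origin + 84k, ±14

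| Origin | First contact | Second contact |
|---|---|---|
| Last dose | Day 84 (70–98) | Day 168 (154–182) |
| 30-day visit on Day 30 | Day 114 (100–128) | Day 198 (184–212) |
| 30-day visit on Day 37 | Day 121 (107–135) | Day 205 (191–219) |

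So about one contact usually falls between the safety visit and Day 130. From a Day 37 visit even that one can fall after Day 130. Whichever origin applies, the contact has no adverse-event content, and where it falls before Day 130 no further contact is due until the window has closed.

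**Which primary safety components are exposed** (8.4.2)
- DLTs: defined on Cycle 1, 21 days (5.2.2). Not exposed.
- Discontinuation of treatment due to an AE: cannot arise after treatment has ended. Not exposed.
- AEs: exposed for new serious events and ECIs from about Day 31 to Day 130. Deaths are picked up by survival follow-up, which leaves non-fatal SAEs and ECIs.

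**ECIs** (7.2.3.2). Two are listed: overdose without symptoms or abnormal laboratory results, which is tied to dosing, and a hepatic laboratory pattern. The latter needs a blood test, and none is scheduled after the 30-day visit. It can surface only through unscheduled testing.

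**The case against.** The strongest reply is that collection does not depend on the schedule. Section 7.2.3.1 obliges the investigator to report any SAE or death within 24 hours throughout the window, related or not, and related SAEs that come to attention even outside it. Section 7.1.1.7.2 has medications for reportable SAEs and ECIs recorded after the 30-day visit. Section 5.8.1 says important clinical-event data must be collected to the last scheduled follow-up.

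These provisions stand, but they do not close the gap. The 24-hour duty governs events the site knows of; it does not make the site ask. Section 5.8.1 refers back to the Schedule of Activities, which has no such item.

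A second reply is that there are other late contacts. Section 7.1.2.7.1 asks for imaging every 9 weeks in subjects who stop without documented progression. Section 7.1.5.5 follows AEs above Grade 1 until they resolve to Grade 0–1 or a new therapy begins. This is right, and the survival call is therefore not the only later contact. But the imaging carries no specified AE inquiry, and following a recorded AE does not look for new ones.

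Third, a telephone question cannot detect a hepatic ECI that nobody has tested for. That also stands; a question can only bring out results of tests done elsewhere.

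Fourth, call scripts and data-entry guidelines are separate documents that I have not seen. One may already contain an SAE prompt. The protocol does not require it.

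**Conclusion.** The mismatch is real and the same in Part I and Part II. For subjects who start no new anticancer therapy, 93 to 100 of the 130 days (72% to 77%) have no scheduled adverse-event inquiry. New non-fatal SAEs in that period depend on passive reporting, in a trial that expects late immune events.

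A reader might infer more, and the documents do not support it:
- **That late events are left to chance.** A binding reporting duty and some incidental contact exist; what is missing is a scheduled prompt.
- **That the primary safety endpoint as a whole is biased.** Only its AE component is exposed. Because it counts subjects with AEs, a late SAE changes the overall proportion only in a subject with no earlier AE. The effect is on the SAE and event-specific summaries, for which Sections 8.4.2 and 8.6.2 state no time window.
- **That 72% to 77% of late events are missed.** These are shares of calendar time. Neither the late SAE rate nor the completeness of passive reporting is given, so no count of missed events can be derived.
- **That under-counting is worst after progression.** Those subjects lose the 9-weekly imaging contact, but any who start new therapy have a 30-day window and essentially no gap. The net direction cannot be established.

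The conclusion rests on reading the schedules as written and on end of treatment coinciding with the last dose. The gap does not depend on the origin of the 12-week clock; only the day of the calls does. This is a cheap improvement to the data, not a flaw that undermines the design.

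**What to change.** - In the Survival Follow-up column of 6.1.4 and 6.2.2, and in the text of 7.1.5.6, add an SAE/ECI inquiry at each contact through the first one on or after Day 130. Each inquiry should cover the time since the last contact, up to Day 130, and ask for any unscheduled liver test results.
- Keep the existing stop at the start of new anticancer therapy.
- State the time origin of the 12-weekly contacts, so that sites know which contact closes the window.

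The cost is one added question on calls already planned, with no new visit or procedure. Reported late SAE counts may rise slightly. The closing question may also come well after Day 130: nominally Day 168 if the clock starts at last dose, or around Day 198 if it starts at a Day 30 visit. Recall is then longer, which is a further reason to fix the origin.
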